### c) Number of Subjects

Up to 80 stable schizophrenia and schizoaffective patients will be recruited from the Mount Sinai Health System Outpatient Departments, and community advertisements.

### d) Study Timelines

The recruitment and enrollment process will be active for approximately 24 months. The anticipated final date for this study is 7/2017. The patients will be informed of the length of the study, which will include 8 visits in total. There will be a screening visit, baseline visit when they will receive the study medication, a visit eight hours after the first dose of medication is taken (baseline) where blood pressure will be checked, 4 weeks of medication administration and weekly monitoring, and a visit eight hours after the dosage of the medication is increased (week 2) where blood pressure will be checked. They will be informed of all of the study procedures for each week, including assessments and medical tests.

### e) Study Endpoints

The primary endpoint related to the efficacy of isradipine will be cognitive enhancement measured by the MATRICS Consensus Cognitive Battery (MCCB). The MCCB is accepted by the FDA as a primary outcome measure for registry trials of cognitive enhancement in schizophrenia.

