### 1) Objectives:

In this project we propose to conduct a 4-week open label cognitive enhancement trial of isradipine in up to 80 stable outpatients with schizophrenia and schizoaffective disorder.

The primary aim of this study is to evaluate the effects of the calcium channel antagonist, isradipine on cognitive dysfunction in patients with schizophrenia and schizoaffective disorder. Incomplete treatment response is common. Cognitive impairment and negative symptoms persist in a majority of patients even when positive psychotic symptoms are well-controlled, and they account for a large proportion of the variance in explaining functional disability (Keefe et al. 2007). This has led to a focused effort to target the specific treatment of cognition in patients with schizophrenia (Green and Nuechterlein, 2004), with somewhat limited success to date.

Novel treatment options have been limited by an incomplete understanding of the biological etiology of schizophrenia; however, recent data from the field of genomics have provided insights into the molecular underpinnings of schizophrenia and its associated symptoms. The majority of genetic risk loci identified to date show trans-disorder effects, increasing susceptibility across a broad range of neuropsychiatric disorders including schizophrenia and bipolar disorder (Williams et al. 2011; Purcell 2009). One possible explanation for this overlap is that several of these genes are influencing risk via their effects on shared phenotypes such as neurocognitive dysfunction. One such example is a single nucleotide polymorphism (SNP; rs1006737) in the calcium channel gene, CACNA1C; initially associated with bipolar illness (Sklar et al. 2008; 2011; Ferreira et al 2008) but also linked with schizophrenia (Green et al. 2009; Nyegaard et al. 2010) and recurrent major depression (Green et al, 2009). The strength of

	Protocol Title:	A Molecular Approach to Treat Cognition in Schizophrenia: Ca 2+ Channel Blockade
	Principal Investigator Name/Contact Info:	[name] [contact]
	Primary Contact Name/Contact Info:	[name] [REDACTED]
	Date Revised:	May 16, 2017
	Study Number:	HSM# 12-0031, GCO# 12-0679, GCO# 13-1987

the association signal for CACNA1C in major mental illness is unambiguous and several subsequent studies have evaluated the effects of CACNA1C variation on neurocognitive capacity.

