### b) Inclusion and Exclusion Criteria

**Inclusion criteria:** **1.** Age 18-60; **2.** DSM-IV schizophrenia or schizoaffective diagnosis; **3.** Residual phase of illness criteria met at screen and baseline as defined by item scores of  $\leq 4$  on each of the Brief Psychiatric Rating Scale (BPRS) hallucinatory behavior, unusual thought content, and conceptual disorganization items; **4.** Hamilton Rating Scale for Depression (HRSD)  $\leq 12$ ; **5.** Baseline Clinician Administered Ratings Scale for Mania (CARS-M) score of  $< 5$ ; **6.** Simpson Angus Scale (SAS) total score of  $\leq 6$ ; **7.** Treatment with at least one but no more than two stably-dosed second-generation antipsychotic medication (other than clozapine) for  $\geq 2$  months and no changes planned over the 4-week study period. First generation antipsychotics and clozapine are thought to cause significant cognitive impairment. Initial baseline cognitive functioning will not be evaluated as inclusion/exclusion criterion because schizophrenia/schizoaffective disorder have a relatively cognitively homogeneous patient sample. We do not anticipate any subjects without cognitive impairment. We will cover for baseline performance to determine if degree of cognitive impairment at baseline is responsible for any change noted.

**Exclusion criteria:** **1.** History of CNS trauma, neurological disorder, ADHD, mental retardation, learning disability, or other non-schizophrenic cause of cognitive impairment; **2.** DSM-IV diagnosis of substance abuse/dependence within 3 months or positive urine toxicology at screening that is not consistent with what participant reported. Substance abuse and dependence are determined based on an extremely comprehensive interview (the SCID), which evaluates lifetime history and current history of all substance use disorders. As per the protocol, DSM-IV diagnosis of substance abuse or dependence within 3 months will be exclusionary (not substance use); **3.** Pregnant women or women of child bearing potential who are not using a medically accepted means of contraception (including oral contraceptive or implant, condom, diaphragm, spermicide, intrauterine device, tubal ligation, or partner with vasectomy) **4.** Women who are breastfeeding; **5.** Active, unstable medical problem that may interfere with cognition; **6.** Current treatment for hypertension; **7.** Uncontrolled hypertension; **8.** History of heart

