### f) Procedures Involved in the Human Research

All eligible subjects will undergo visits at screening, baseline (week 0), visit 8 hours after week 0, week 1, week 2, visit 8 hours after week 2, week 3, and week 4 (end of study). The parameters of study drug dosing are as follows: isradipine as utilized in this trial will be administered twice daily. Isradipine will be titrated as follows: baseline (week 0) 5 mg/day BID; Week 2 increase to 10 mg/day BID if 5 mg was well-tolerated. Dosing will be flexible based on side effects with a maximum=10 mg/day. If 5 mg cannot be tolerated, the subject will be discontinued. Dosing was based on package labeling for hypertension and prior studies in Parkinson's disease (Simuni et al. 2010).

	Protocol Title:	A Molecular Approach to Treat Cognition in Schizophrenia: Ca 2+ Channel Blockade
	Principal Investigator Name/Contact Info:	[name] [contact]
	Primary Contact Name/Contact Info:	[name] [REDACTED]
	Date Revised:	May 16, 2017
	Study Number:	HSM# 12-0031, GCO# 12-0679, GCO# 13-1987

Measures described in detail below:

Safety Outcome Measures

- The Side Effects Checklist (SEC; physician administered) and side effect self-report form – (all visits)
- Vital signs including blood pressure (standing/supine – all visits)
- Blood pressure check within 8 hours of first dose. Staff contact number will be given to subject in case there are any problems before the 8 hour BP check (week 0). An additional blood pressure check 8 hours after increased dosage (week 2).
- Electrocardiogram (ECG); chemistry panel and CBC via blood draw (approximately 2 TSP blood drawn); urinalysis (screening & week 4)
- Urine toxicology (screening)
- Urine pregnancy test for women of childbearing potential (baseline)
- Abnormal Involuntary Movement Scale (AIMS) and Simpson Angus Scale (SAS) (all visits)
- Beck Scale for Suicidal Ideation (SSI) and Columbia Suicide Severity Rating Scale (C-SSRS) (all visits)

Clinical/Symptom Measures

- Structured Clinical Interview for the DSM-IV (SCID-IV) (screening)
- Symptom rating scales including the Brief Psychiatric Rating Scale (BPRS), the Scale for the Assessment of Negative Symptoms (SANS), the Hamilton Rating Scale for Depression (HRSD), the Clinical Global Impression Scale (CGI), the Clinician Administered Rating Scale for Mania (CARS-M) (all visits)

Neurocognitive/Functional Measures

- MATRICS Consensus Cognitive Battery\* (baseline & week 4)

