Data from this study may be used in medical publications or presentations. The information will be de-identified so that individual subjects cannot be recognized and the information will no longer be considered PHI. The information that is collected for research will be analyzed for many years and it is not possible to know how long this analysis and follow-up will take. Therefore, participants are allowing access to this information indefinitely.

Subjects will only be identified with a numerical code in compliance with HIPAA regulations. Raw subject data will be secured in double locked physical control. Digitized raw data will be similarly de-identified using coding and will be secured on an MS SQL server with Windows integrated security.

	Protocol Title:	A Molecular Approach to Treat Cognition in Schizophrenia: Ca 2+ Channel Blockade
	Principal Investigator Name/Contact Info:	[name] [contact]
	Primary Contact Name/Contact Info	[name] [REDACTED]
	Date Revised:	May 16, 2017
	Study Number:	HSM# 12-0031, GCO# 12-0679, GCO# 13-1987

Data analysis plan is included below. All analyses will be based on an intent-to-treat sample of subjects who received at least one dose of isradipine. Since the missing values may be dependent on the observed outcomes, we assume the missing data mechanism to be missing at random, and hence a mixed models analysis will be used to assess the treatment effect of isradipine with fixed effects for week and first order autoregressive covariance structure to evaluate change over time for all of the primary outcome measures. Cognitive measures will be handled differently, as these will only be collected at two time points – if missing data are substantial (or a complete visit is missing), subjects' data will not/cannot be meaningfully analyzed.

*Primary Analyses* will test the following hypotheses based on our specific aims:

To determine the feasibility of 4 weeks of isradipine on cognitive outcomes in SZ.  
Hypothesis: We will successfully recruit up to 80 stable schizophrenia and schizoaffective patients

To determine the safety of 4 weeks of isradipine on cognitive outcomes in SZ.  
Hypothesis: The frequency of new or worsened side effects (clinician-rated; self-reported; lab-based) will not be significantly different from baseline to end of study visit.

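### The aim, endpoint and analysis wording treat uncontrolled MCCB change as an isradipine effect, and the baseline-impairment question cannot be answered in this design

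*Combined protocol and SAP*

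**What the plan says.** Section 1 (Objectives) sets the design: "we propose to conduct a 4-week open label cognitive enhancement trial of isradipine". It then gives the aim: "The primary aim of this study is to evaluate the effects of the calcium channel antagonist, isradipine on cognitive dysfunction in patients". Section 5e makes the MCCB the efficacy endpoint: "The primary endpoint related to the efficacy of isradipine will be cognitive enhancement measured by the MATRICS Consensus Cognitive Battery (MCCB".

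Section 5f schedules the MCCB at "baseline & week 4" and puts all eligible subjects on the same isradipine schedule. Table 1 there lists ten MCCB tests in seven domains and two additional measures. It does not define a composite score.

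The analysis plan is in Section 5h. The analysis set is: "All analyses will be based on an intent-to-treat sample of subjects who received at least one dose of isradipine". The model is described so: "a mixed models analysis will be used to assess the treatment effect of isradipine with fixed effects for week". It is said to serve all of the primary outcome measures. A sentence on cognition follows: "Cognitive measures will be handled differently, as these will only be collected at two time points". That sentence goes on to say what happens when data are missing. The hypotheses listed under Primary Analyses concern feasibility and safety, and none concerns the MCCB.

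Section 5b does not make baseline cognition an entry criterion, and adds: "We will cover for baseline performance to determine if degree of cognitive impairment at baseline is responsible for any change noted".

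**The concern.** No comparator, untreated lead-in, practice session before baseline, alternate test forms or retest correction is described. Every patient starts isradipine, knows it, takes the test a second time and is four weeks older, all between the same two assessments. A mean MCCB gain under this plan could be reported as efficacy when an inert drug would have produced it.

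Section 5b raises a related problem. A relation between baseline score and change could be reported as showing that baseline impairment was responsible for the change, when imperfect test reliability is enough to produce it.

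Section 8 says the results could support larger pivotal trials, so the reading given to an MCCB gain bears on the decision to continue.

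**Working it through.** **Figures in the plan.** There is none to reproduce. The documents give no significance level, power, effect size, SD, retest correlation or retest gain, and the ceiling of 80 patients has no derivation.

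**What the design identifies.** Mean change from baseline to week 4 = drug + retest + expectancy + time. All four are present for every patient over the same interval. There is one observed mean and there are four unknowns. More patients, or covariates such as baseline score or chlorpromazine equivalents, do not add the missing contrast. The same holds for a week term in a mixed model fitted to treated patients only: it estimates change over time.

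**Illustration 1: mean change.** Apart from the ceiling of 80 patients, all inputs are assumptions: drug effect zero; equal variance at both visits; retest correlation r = 0.7, 0.8 or 0.9; total non-drug gain g in baseline SD units; two-sided 5% paired t-test.

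- SD of change = √(2(1−r)) = 0.775, 0.632, 0.447.
- Noncentrality at n = 80 and g = 0.2 is 0.2 × √80 / SD of change = 2.31, 2.83, 4.00.
- The noncentral t distribution then gives these probabilities of a significant result:

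| n | g | r = 0.7 | r = 0.8 | r = 0.9 |
|---|---|---|---|---|
| 80 | 0.1 | 21% | 29% | 51% |
| 80 | 0.2 | 63% | 80% | 98% |
| 60 | 0.2 | 50% | 67% | 93% |
| 40 | 0.2 | 36% | 50% | 79% |

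With g = 0 the rate is the nominal 5%. The smallest significant mean change at n = 80 is 1.99 × SD of change / √80 = 0.17, 0.14 and 0.10 SD. A non-drug change above that size is more likely than not to appear as a significant improvement.

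**Illustration 2: baseline and change.** Same assumptions, with no effect of any kind (g = 0) and unit variances.

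- Covariance of change with baseline = r − 1, so the slope of change on baseline is −(1−r) = −0.30, −0.20, −0.10.
- Correlation = −(1−r)/√(2(1−r)) = −√((1−r)/2) = −0.39, −0.32, −0.22.
- At n = 80 a correlation is significant beyond 1.99/√(78 + 1.99²) = 0.22 in absolute value.
- In 20,000 simulated trials per value of r, the correlation was significant in about 95%, 82% and 52%.

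Regressing week 4 on baseline does not help. The baseline coefficient is then r, which differs from zero because the test is reliable and says nothing about what caused change.

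**The case against.** The strongest defence is that this is a small preparatory study and largely presents itself as one. Open label stands in the first sentence of Section 1, the listed hypotheses are feasibility and safety, and Section 8 hedges on benefit. No passage commits the investigators to attributing an MCCB gain to isradipine. This stands as a limit on the consequence. It does not withdraw the wording of Sections 1 and 5e, and no section states the limitation.

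Four stronger readings are tempting, and the documents do not support them.

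- *That Section 5h clearly removes cognition from the mixed model, leaving the MCCB with no analysis and making the model a separate fault for other outcomes.* The section is ambiguous. The model is for all primary outcome measures, and Section 5e makes the MCCB primary. The sentence on different handling may be only a missing-data rule. The treatment-effect wording is wrong on either reading.
- *That the investigators plan to claim greater benefit in more impaired patients.* Section 5b does not say so. It can be read as checking a non-drug explanation of change. The question is unanswerable in this design on either reading.
- *That regression to the mean inflates the average MCCB change.* Cognition is not an entry criterion, so no such shift in the mean is claimed. Regression to the mean matters here only for the baseline slope.
- *That outcomes have been examined as the trial went along.* Section 5h describes a data-quality check after every five completed subjects. That is weak evidence of looking at results.

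That there is one arm is an inference from the absence of any comparator and from the analysis set. The documents do not use the term.

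**Conclusion.** The concern holds as a fault of wording and interpretation. As written, Sections 1, 5e and 5h describe uncontrolled within-subject change as an effect, efficacy or treatment effect of isradipine, which the design cannot show. Section 5b sets a question that the design cannot answer. This follows from the design alone and needs no numerical assumption.

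The percentages show sensitivity only. They rest on an assumed retest correlation of 0.7 to 0.9, an assumed non-drug gain, equal variances, a paired t-test and 80 completers. With fewer completers or a smaller gain they fall, as the table shows.

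A reader might infer that the trial as a whole is unsound. It is not: one open-label arm can serve feasibility and descriptive safety. The point should be fixed because it touches the stated primary aim and the correction is nearly free.

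**What to change.** 1. **Sections 1, 5e and 5h.** Replace the effect, efficacy and treatment-effect wording with *uncontrolled within-subject change from baseline*.
2. **MCCB summary.** Before analysis, the sponsor names one MCCB score, since none is defined. Report week 4 minus baseline for it, with a 95% confidence interval and the number of patients with both assessments. State the date on which this was specified.
3. **Interpretation.** State that the change cannot be attributed to isradipine. If the lower confidence limit is above zero, add that a total non-drug change (retest, expectancy and time together) as large as that limit would remove significance. Subtracting the limit from the mean puts the new lower limit exactly at zero, where p = 0.05.
4. **Section 5b.** Replace the language of responsibility with an exploratory description of the association between baseline and change, labelled as subject to regression to the mean.

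The cost is wording in four sections and one added summary line. The document is dated May 16, 2017 and Section 5d expects the study to end in 7/2017, so no control arm is asked for. The price is a less favourable efficacy statement, an MCCB summary that must be labelled as specified late, and no confirmatory answer on dependence on baseline.

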### f) Procedures Involved in the Human Research

All eligible subjects will undergo visits at screening, baseline (week 0), visit 8 hours after week 0, week 1, week 2, visit 8 hours after week 2, week 3, and week 4 (end of study). The parameters of study drug dosing are as follows: isradipine as utilized in this trial will be administered twice daily. Isradipine will be titrated as follows: baseline (week 0) 5 mg/day BID; Week 2 increase to 10 mg/day BID if 5 mg was well-tolerated. Dosing will be flexible based on side effects with a maximum=10 mg/day. If 5 mg cannot be tolerated, the subject will be discontinued. Dosing was based on package labeling for hypertension and prior studies in Parkinson's disease (Simuni et al. 2010).

	Protocol Title:	A Molecular Approach to Treat Cognition in Schizophrenia: Ca 2+ Channel Blockade
	Principal Investigator Name/Contact Info:	[name] [contact]
	Primary Contact Name/Contact Info:	[name] [REDACTED]
	Date Revised:	May 16, 2017
	Study Number:	HSM# 12-0031, GCO# 12-0679, GCO# 13-1987

Measures described in detail below:

Safety Outcome Measures

- The Side Effects Checklist (SEC; physician administered) and side effect self-report form – (all visits)
- Vital signs including blood pressure (standing/supine – all visits)
- Blood pressure check within 8 hours of first dose. Staff contact number will be given to subject in case there are any problems before the 8 hour BP check (week 0). An additional blood pressure check 8 hours after increased dosage (week 2).
- Electrocardiogram (ECG); chemistry panel and CBC via blood draw (approximately 2 TSP blood drawn); urinalysis (screening & week 4)
- Urine toxicology (screening)
- Urine pregnancy test for women of childbearing potential (baseline)
- Abnormal Involuntary Movement Scale (AIMS) and Simpson Angus Scale (SAS) (all visits)
- Beck Scale for Suicidal Ideation (SSI) and Columbia Suicide Severity Rating Scale (C-SSRS) (all visits)

Clinical/Symptom Measures

- Structured Clinical Interview for the DSM-IV (SCID-IV) (screening)
- Symptom rating scales including the Brief Psychiatric Rating Scale (BPRS), the Scale for the Assessment of Negative Symptoms (SANS), the Hamilton Rating Scale for Depression (HRSD), the Clinical Global Impression Scale (CGI), the Clinician Administered Rating Scale for Mania (CARS-M) (all visits)

Neurocognitive/Functional Measures

- MATRICS Consensus Cognitive Battery\* (baseline & week 4)
- UCSD Performance Skills Assessment (UPSA) (baseline & week 4)
- Quality of Life Scale (QoL) (baseline & week 4)

	Protocol Title:	A Molecular Approach to Treat Cognition in Schizophrenia: Ca 2+ Channel Blockade
	Principal Investigator Name/Contact Info:	[name] [contact]
	Primary Contact Name/Contact Info	[name] [REDACTED]
	Date Revised:	May 16, 2017
	Study Number:	HSM# 12-0031, GCO# 12-0679, GCO# 13-1987

\* **Table 1.**

The MATRICS Consensus Cognitive Battery	Domain	Note/Description
Category Fluency	Speed of Processing	Total animals in 60 seconds
BACS Symbol Coding	Speed of Processing	Matching numbers to symbols
Trail Making Test Part A	Speed of Processing	Dot-to-dot: Numbers only
CPT-Identical Pairs	Attention/Vigilance	Computerized numeric stimuli
Letter-Number Span	Working Memory	Recoding numbers and letters in order
WMS-III Spatial Span	Working Memory	Visual sequence forward and backward
Hopkins Verbal Learning (HVLT)	Verbal Learning	12 word list x 3
Brief Visuospatial Memory Test (BVMT)	Visual Learning	6 designs to be drawn from recall
NAB Mazes	Reasoning & Prob Solving	Pencil-paper maze solutions
MSCEIT Managing Emotions	Social Cognition	Situational social judgments
Additional Measures (“Plus”)	---	---
Affective Go-no-go	Affective Neuroscience	Emotional modulation of inhibition
Emotional Stroop	Affective Neuroscience	Affective Bias/Cognitive Control

**g) Specimen Banking**

N/A

	Protocol Title:	A Molecular Approach to Treat Cognition in Schizophrenia: Ca 2+ Channel Blockade
	Principal Investigator Name/Contact Info:	[name] [contact]
	Primary Contact Name/Contact Info	[name] [REDACTED]
	Date Revised:	May 16, 2017
	Study Number:	HSM# 12-0031, GCO# 12-0679, GCO# 13-1987

